7.3.4 Additional Protocol-Specific Expedited Adverse Event Reporting Exclusions

For this protocol only, the AEs/grades listed below *do not* require expedited reporting via CTEP-AERS. However, they still must be reported through the routine reporting mechanism (Section 7.4):

CTCAE SOC	Adverse Event	CTCAE Grade at which the event will not require expedited reporting ¹
Investigations	Neutrophil count decreased	\leq Grade 4
	Platelet count decreased	\leq Grade 4
	White blood count	\leq Grade 4
	Lymphocyte count decreased	≤ Grade 4
Blood and lymphatic system disorders	Anemia	≤ Grade 4

¹ These exceptions only apply if the adverse event does not result in hospitalization. If the adverse event results in hospitalization, then the standard expedited adverse events reporting requirements must be followed.

Specific protocol exceptions to expedited reporting should be reported expeditiously by investigators **ONLY** if they exceed the expected grade of the event.

The following hospitalizations are not considered to be SAEs because there is no "adverse event" (*i.e.*, there is no untoward medical occurrence) associated with the hospitalization:

- Hospitalizations for respite care
- Planned hospitalizations required by the protocol
- Hospitalization planned before informed consent (where the condition requiring the hospitalization has not changed post study drug administration)
- Hospitalization for elective procedures unrelated to the current disease and/or treatment on this trial
- Hospitalization for administration of study drug or insertion of access for administration of study drug
- Hospitalization for routine maintenance of a device (*e.g.*, battery replacement) that was in place before study entry
- Hospitalization, or other serious outcomes, for signs and symptoms of progression of the cancer.

7.4 Routine Adverse Event Reporting

All Adverse Events **must** be reported in routine study data submissions. **AEs reported expeditiously through CTEP-AERS must** also be reported in routine study data submissions.

Adverse event data collection and reporting, which are required as part of every clinical trial, are done to ensure the safety of patients enrolled in the studies as well as those who will enroll in future studies using similar agents. AEs are reported in a routine manner at scheduled times during the trial using Medidata Rave. For this trial the Adverse Event CRF is used for routine AE reporting in Rave.

7.5 Secondary Malignancy

A *secondary malignancy* is a cancer caused by treatment for a previous malignancy (*e.g.*, treatment with investigational agent/intervention, radiation or chemotherapy). A secondary malignancy is not considered a metastasis of the initial neoplasm.

CTEP requires all secondary malignancies that occur following treatment with an agent under an NCI IND/IDE be reported expeditiously via CTEP-AERS. Three options are available to describe the event:

- Leukemia secondary to oncology chemotherapy (*e.g.*, acute myelocytic leukemia [AML])
- Myelodysplastic syndrome (MDS)
- Treatment-related secondary malignancy

Any malignancy possibly related to cancer treatment (including AML/MDS) should also be reported via the routine reporting mechanisms outlined in each protocol.

7.6 Second Malignancy

A second malignancy is one unrelated to the treatment of a prior malignancy (and is **NOT** a metastasis from the initial malignancy). Second malignancies require **ONLY** routine AE reporting unless otherwise specified.

8. PHARMACEUTICAL INFORMATION

A list of the adverse events and potential risks associated with the investigational agents administered in this study can be found in Section 7.1.

8.1 CTEP IND Agent(s)

8.1.1 CDX-1127 (Varlilumab; NSC 778372)

Other Names: CDX-1127 (Varlilumab)

Classification: monoclonal antibody of the IgG1k isotope

M.W.: 146,076 Dalton

Mode of Action: CDX-1127 (Varlilumab) binds to human CD27 and acts as an agonist of CD27, reacting with the ligand binding site of CD27 as demonstrated by inhibition of CD70 binding to CD27. CDX-1127 (Varlilumab) does not bind other tumor necrosis factor receptor (TNFR) family members. CDX-1127 (Varlilumab) does not lead to direct activation of lymphocytes in the absence of signaling through the T cell receptor (TCR).

Description: CDX-1127 (Varlilumab) is a recombinant, fully human monoclonal antibody (mAb) of the IgG1 κ isotype that specifically binds human CD27. The amino acid sequence of CDX-1127 (varlilumab) has been determined and its structure is comprised of two IgG1 heavy chains and two kappa light chains which are disulfide-linked as expected for a mAb.

How Supplied: CDX-1127 (Varlilumab) is formulated as a clear, colorless, sterile solution intended for single-use parenteral administration. Each vial contains a nominal 50 mg CDX-1127 (varlilumab) protein in a 10.0 mL volume of buffered solution composed of Sodium Phosphate, Potassium Phosphate, Potassium Chloride, Sodium Chloride, and Polysorbate 80 with a pH of 7.0.

Preparation: Withdraw the prescribed dose of CDX-1127 (varlilumab) from the required number of vials. CDX-1127 (varlilumab) may be added to empty non-PVC/non-DEHP or PVC IV bags and administered undiluted or further diluted with 0.9% sodium chloride in a non-PVC/non-DEHP IV bag to a concentration between 0.27 mg/mL and 5 mg/mL or a PVC IV bag to a concentration between 0.1 mg/mL and 5 mg/mL. Gently invert the infusion bag 5 times to thoroughly mix the CDX-1127 (varlilumab) and 0.9% sodium chloride.

Storage: Store at 2 - 8°C (36 - 46°F). CDX-1127 (Varlilumab) should be protected from light. However, sufficient light protection is provided by the secondary container (carton); no specific light protection is needed during preparation of the dosing solution and infusion.

If a storage temperature excursion is identified, promptly return CDX-1127 (varlilumab) to 2 - 8°C (36 - 46°F) and quarantine the supplies. Provide a detailed report of the excursion (including documentation of temperature monitoring and duration of the excursion) to [contact] for determination of suitability.

Stability: Stability studies are ongoing.

CAUTION: Once the sterile vials are entered (i.e., once CDX-1127 (varlilumab) is drawn into a syringe), the drug should be used as soon as possible (typically within 3 hours if kept at room temperature or within 6 hours if refrigerated; or in accordance with any applicable institutional guidance).

Route(s) of Administration: IV

Method of Administration: Infuse CDX-1127 (varlilumab) intravenously over 90 minutes using a polyethylene- or polypropylene-lined, non-DEHP-containing, low-protein binding/low-sorbing administration set with a 0.2 or 0.22 micron polyethersulfone (PES) in-line filter.

Patient Care Implications: It is possible that CDX-1127 (varlilumab) may exacerbate autoimmune diseases. Therefore, with the exception of vitiligo, CDX-1127 (varlilumab) should not be administered to patients with autoimmune diseases.

Management of CDX-1127(varlilumab) induced irAEs, should they occur, should be based on the extensive experience with treatment of toxicities related to ipilimumab and other checkpoint blockers. Guidelines and algorithms have been published for treatment of ipilimumab related toxicity (see ipilimumab package insert) and investigators should be familiar with these recommendations in the event of CDX-1127 induced irAEs (Di Giacomo, Biagioli et al. 2010; Kaehler, Piel et al. 2010).

Availability: Varlilumab is an investigational agent supplied to investigators by the Division of Cancer Treatment and Diagnosis (DCTD), NCI.

Varlilumab is provided to the NCI under a Collaborative Agreement between the Pharmaceutical Collaborator and the DCTD, NCI (see Section 12.4).

8.1.2 Nivolumab (NSC 748726)

Amino Acid Sequence: 4 polypeptide chains, which include 2 identical heavy chains with 440 amino acids and 2 identical light chains.

Other Names: BMS-936558, MDX1106

Classification: Anti-PD-1MAb

M.W.: 146,221 Daltons

Mode of Action: Nivolumab targets the programmed death–1 (PD-1, cluster of differentiation 279 [CD279]) cell surface membrane receptor. PD-1 is a negative regulatory receptor expressed by activated T and B lymphocytes. Binding of PD-1 to its ligands, programmed death–ligand 1 (PD-L1) and 2 (PD-L2), results in the down-regulation of lymphocyte activation. Nivolumab inhibits the binding of PD-1 to PD-L1 and PD-L2. Inhibition of the interaction between PD-1 and its ligands promotes immune responses and antigen-specific T-cell responses to both foreign antigens as well as self-antigens.

Description: Nivolumab Injection is a clear to opalescent, colorless to pale yellow

liquid; light (few) particulates may be present. The drug product is a sterile, nonpyrogenic, single-use, isotonic aqueous solution formulated in sodium citrate dihydrate, sodium chloride, mannitol, diethylenetriamine pentacetic acid (pentetic acid) and polysorbate 80 (Tween[®] 80), and water for injection. Dilute solutions of hydrochloric acid and/or sodium hydroxide may be used for pH adjustment (pH 5.5-6.5)..

How Supplied: Nivolumab is supplied by Bristol-Myers Squibb and distributed by the Pharmaceutical Management Branch, CTEP/DCTD/NCI as 100 mg vials (10 mg/mL) with a 0.7 mL overfill. It is supplied in 10 mL type I flint glass vials, with fluoropolymer film-laminated rubber stoppers and aluminum seals.

Preparation: Nivolumab injection can be infused undiluted (10 mg/mL) or diluted with 0.9% Sodium Chloride Injection, USP or 5% Dextrose, USP. When the dose is based on patient weight (i.e., mg/kg), nivolumab injection can be infused undiluted or diluted to protein concentrations as low as 0.35 mg/mL. When the dose is fixed (eg, 240 mg, 360 mg, or 480 mg flat dose), nivolumab injection can be infused undiluted or diluted so as not to exceed a total infusion volume of 160 mL. For patients weighing less than 40 kilograms (kg), the total

volume of infusion must not exceed 4 mL per kg of patient weight. During drug product preparation and handling, vigorous mixing or shaking is to be avoided.

Nivolumab infusions are compatible with polyvinyl chloride (PVC) or polyolefin containers and infusion sets, and glass bottles.

Storage: Vials of Nivolumab injection must be stored at 2°-8°C (36°-46°F) and protected from light, freezing, and shaking. The unopened vials can be stored at room temperature (up to 25°C, 77°F) and room light for up to 48 hours. If a storage temperature excursion is identified, promptly return Nivolumab to 2°C-8°C and quarantine the supplies. Provide a detailed report of the excursion (including documentation of temperature monitoring and duration of the excursion) to [contact] for determination of suitability.

Stability: Shelf-life surveillance of the intact vials is ongoing.

The administration of undiluted and diluted solutions of Nivolumab must be completed within 24 hours of preparation. If not used immediately, the infusion solution may be stored up to 24 hours in a refrigerator at $2^{\circ}-8^{\circ}C$ ($36^{\circ}-46^{\circ}F$) and a maximum of 8 hours of the total 24 hours can be at room temperature ($20^{\circ}-25^{\circ}C$, $68^{\circ}-77^{\circ}F$) and room light. The maximum -8 hour period under room temperature and room light conditions includes the product administration period.

CAUTION: The single-use dosage form contains no antibacterial preservative or bacteriostatic agent. Therefore, it is advised that the product be discarded 8 hours after initial entry.

Route of Administration: Intravenous infusion over 30 minutes. Do not administer as

an IV push or bolus injection.

Method of Administration: Administer through a 0.2 micron to 1.2 micron pore size, low-protein binding polyethersulfone membrane in-line filter. Nivolumab infusions are compatible with polyvinyl chloride (PVC) or polyolefin containers and infusion sets, and glass bottles.

Potential Drug Interactions: None have been reported.

Potential Drug Interactions: The indirect drug-drug interaction potential of nivolumab was assessed using systemic cytokine modulation data for cytokines known to modulate CYP enzymes. There were no meaningful changes in cytokines known to have indirect effects on CYP enzymes across all dose levels of nivolumab. This lack of cytokine modulation suggests that nivolumab has no or low potential for modulating CYP enzymes, thereby indicating a low risk of therapeutic protein-drug interaction.

Patient Care Implications: Women of childbearing potential (WOCBP) receiving nivolumab must continue contraception for a period of 5 months after the last dose of nivolumab. Men receiving nivolumab and who are sexually active with WOCBP must continue contraception for a period of 7 months after the last dose of nivolumab.

Availability: Nivolumab is an investigational agent supplied to investigators by the Division of Cancer Treatment and Diagnosis (DCTD), NCI.

Nivolumab is provided to the NCI under a Collaborative Agreement between the Pharmaceutical Collaborator and the DCTD, NCI (see Section 12.4).

8.1.3 Agent Ordering and Agent Accountability

8.1.3.1 NCI-supplied agents may be requested by the Principal Investigator (or their authorized designee) at each participating institution. Pharmaceutical Management Branch (PMB) policy requires that agent be shipped directly to the institution where the patient is to be treated. PMB does not permit the transfer of agents between institutions (unless prior approval from PMB is obtained). The CTEP-assigned protocol number must be used for ordering all CTEP-supplied investigational agents. The responsible investigator at each participating institution must be registered with CTEP, DCTD through an annual submission of FDA Form 1572 (Statement of Investigator), Curriculum Vitae, Supplemental Investigator Data Form (IDF), and Financial Disclosure Form (FDF). If there are several participating investigators at one institution, CTEP-supplied investigator at that institution.

Supplies may be ordered once a patient has been enrolled to the study; starter supplies of investigational agents are not available.

Active CTEP-registered investigators and investigator-designated shipping designees and ordering designees can submit agent requests through the PMB Online Agent Order Processing (OAOP) application. Access to OAOP requires the establishment of a CTEP Identity and Access Management (IAM) account and the maintenance of an "active" account status and a "current" password. For questions about drug orders, transfers, returns, or accountability, call or email PMB any time. Refer to the PMB's website for specific policies and guidelines related to agent management.

- 8.1.3.2 Agent Inventory Records The investigator, or a responsible party designated by the investigator, must maintain a careful record of the receipt, dispensing and final disposition of all agents received from the PMB using the appropriate NCI Investigational Agent (Drug) Accountability Record (DARF) available on the CTEP forms page. Store and maintain separate NCI Investigational Agent Accountability Records for each agent, strength, formulation and ordering investigator on this protocol.

9. BIOMARKER, CORRELATIVE, AND SPECIAL STUDIES

9.1 Specimen Requirements for Correlative Studies

In this study, we propose several correlative studies, as detailed below. These assays are

specifically chosen to provide information on the status of the immune system in general as well as specific information related to the mechanism of action of the study drugs. One integrated biomarker study (CD27 by IHC) has been included which has been approved by the Biomarker Review Committee (BRC) of the Cancer Therapy Evaluation Program (CTEP). All other correlative studies will be exploratory in nature. Although exploratory, the proposed studies will be done on specimens obtained at time points relevant to standard clinical practice (prior to treatment, and at the time of suspected progression) in order to avoid unnecessary risks. The scientific information obtained from these studies is intended to be hypothesis-generating and will help us advance our understanding of the anti-tumoral immune system in the context of simultaneous manipulations using immunomodulatory drugs in lymphoma.

Submission of tumor tissue obtained from a biopsy performed within 60 days of registration is a mandatory part of this protocol. This tissue will be used to confirm the diagnosis and correctly stratify patients between categories A or B (Section 3.1.1). Submission of tumor tissue obtained from a biopsy performed to at the time of suspected disease progression is optional, except for Group 1 patients who cross over to Group 2, for these patients, the biopsy is mandatory. The importance of a repeat biopsy for patients in Group 1 who are suspected to have progressive disease is explained by the fact that responses to immunotherapy drugs may differ from those of standard cytotoxic treatments. Before proceeding with additional therapy we must exclude pseudo-progression and delayed responses by obtaining a repeat biopsy.

The biopsies obtained at the time of progression for patients in Group 2 or for those in Group 1 not wishing to cross-over to Group 2 are exploratory in nature. We anticipate that these biopsies will be done in approximately 25% of patients (some for this study and some also for eligibility in subsequent trials). Even though the cohort may be small, we may potentially gain insights into whether patients progress despite increased immune cell infiltration into the tumor.

All tumor biopsy tissue will be submitted in formalin-fixed paraffin-embedded (FFPE) format to the Mayo Clinic where biomarker specimen processing will be centralized. Once the quality of the specimen is verified by expert hematopathologist, ten 4 micron unstained slides will be forwarded to Mosaic Laboratories (Lake Forest, CA) for CD27 IHC assay (integrated biomarker). The remaining tissue block or slides will be used to generate specimens for exploratory biomarker studies including (1) additional unstained slides for IHC evaluation of intra-tumoral immune cells, (2) extraction of tumor DNA for whole-exome sequencing, (3) evaluation of 9p24.1 locus by FISH and (4) mass cytometry analysis of intra-tumoral immune cells all of which will be performed centrally at Mayo Clinic.

Serial collection of peripheral blood is also mandatory for patients participating in this study. Peripheral blood will be collected at baseline and every 14 days (prior to administration of study drugs) for the first 12 weeks on study. Submission of peripheral blood obtained at the time of disease progression is optional. Peripheral blood will be used to generate serum for cytokine profiling, isolation of peripheral blood mononuclear

cells for immunophenotyping, immunogenicity assays and pharmacokinetic studies.

Any surplus of tissue, DNA, cells or serum will be banked at Mayo Clinic for additional studies for the patients who provide additional consent for tissue banking. If consent for banking was not provided by the patient, the remaining blocks or slides will be returned to the original institution after minimum specimens are generated. Surplus of blood, plasma, serum, DNA and cells will be discarded once the minimum specimens are generated if the patient did not provide consent for banking of specimens.

Integrated Correlative Study

Correlative Study	Optional or Mandatory	Required Specimen	Collection Timepoints
	Mandatory	FFPE blocks (preferred) or 3 unstained glass slides with 4-micron-thick sections from FFPE blocks	For all patients: Baseline (Within 60 days of registration)
Quantification/ Characterization of CD27+ cells by IHC	Mandatory	FFPE blocks (preferred) or 3 unstained glass slides with 4-micron-thick sections from FFPE	For patients who cross over from Group 1 to Group 2 only: At the time of progression
	Optional	FFPE blocks (preferred) or 3 unstained glass slides with 4-micron-thick sections from FFPE	At the end of study (for all patients)

Exploratory Correlative Studies

Correlative Study	Optional or Mandatory	Required Specimen	Collection Timepoints
Analysis of Peripheral Blood Immune Cells by Mass Cytometry (CyTOF) ¹	Mandatory	Peripheral blood 12 mL collected in yellow top tubes (ACD)	Baseline and every 14 days for the first 12 weeks of treatment

Identification/ Characterization of Intratumoral Immune Cells by IHC and CyTOF	Mandatory	FFPE blocks (preferred) or 7 unstained glass slides with 4- micron-thick sections from FFPE	For all patients: Baseline (Within 60 days of registration)
	Mandatory	FFPE blocks (preferred) or 7 unstained glass slides with 4- micron-thick sections from FFPE	For patients who cross over from Group 1 to Group 2 only: At the time of progression
	Optional	FFPE blocks (preferred) or 7 unstained glass slides with 4- micron-thick sections from FFPE	For all patients: At the end of study
Evaluation of Genetic Alterations of Chromosome 9p24.1 by FISH	Mandatory	FFPE blocks (preferred) or 1 unstained glass slide with 4- micron-thick section from FFPE	For all patients: Baseline (Within 60 days of registration)
	Mandatory	FFPE blocks (preferred) or 1 unstained glass slides with 4- micron-thick section from FFPE	For patients who cross over from Group 1 to Group 2 only: At the time of progression
	Optional	FFPE blocks (preferred) or 1 unstained glass slide with 4- micron-thick sections from FFPE	For all patients: At the time of disease progression
Evaluation of Serum Cytokine Profile by ELISA ¹	Mandatory	10 mL peripheral blood collected in red top tubes (no anticoagulant)	Baseline and every 14 days for the first 12 weeks of treatment

Evaluation of pharmacokinetics and immunogenicity to CDX- 1127 (Varlilumab) ¹	Mandatory	10 mL peripheral blood collected in red top tubes (no anticoagulant)	 Group 2: Baseline, pre-dose every 4 weeks for the first 4 cycles, at the end of treatment, and at safety follow-up (if available). Group 1: Baseline for all patients. Group 1 at cross- over: pre-dose every 4 weeks prior to the first 4 doses of CDX- 1127 (varlilumab), at the end of treatment, and at safety follow- up (if available).
Evaluation of pharmacokinetics and immunogenicity to nivolumab ¹	Mandatory	10 mL peripheral blood collected in red top tubes (no anticoagulant)	For all patients: Baseline, pre-dose every 4 weeks for the first 4 cycles, at the end of treatment, and at safety follow-up (if available).
Evaluation of Mutation Burden by WES	Mandatory	FFPE blocks (preferred) or 2 unstained glass slides with 4- micron-thick sections from FFPE	For all patients: Baseline (Within 60 days of registration)
	Mandatory	FFPE blocks (preferred) or 2 unstained glass slides with 4-micron-thick sections from FFPE	For patients who cross over from Group 1 to Group 2 only: At the time of disease progression

	Optional	FFPE blocks (preferred) or 2 unstained glass slides with 4-micron-thick sections from FFPE	
--	----------	--	--

1. Kits will be provided by Mayo Clinic. To request kits, refer to Appendix E.

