5.4 Duration of Follow Up Following End of Therapy

Patients will be followed for additional 100 days (based on 5 half-lives) after end of therapy or until death, whichever occurs first. Patients removed from therapy for unacceptable adverse event(s) will be followed until resolution or stabilization of the adverse event.

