c.	A pre-study biopsy is mandatory for all groups and must be obtained within 60 days prior to registration. For Group 1 patients who elect to cross over to Group 2, a biopsy is mandatory at that time. An off-study biopsy is optional for all groups.
d:	Off-study evaluation to be performed 30 days (+/- 14 days) after the last dose of study drug. Patients are followed for at least 100 days for AE assessment.
e:	As clinically indicated, perform an evaluation of cardiac function including ECG and echocardiogram for any patients with a history of CHF or at risk because of underlying cardiovascular disease or exposure to cardiotoxic drugs. Also perform an evaluation for patients with evidence of CHF, MI, cardiomyopathy, or myositis including lab tests and cardiology consultations including ECG, echocardiogram, CPK and troponin.
f:	Blood draw for correlative studies will be obtained at baseline (within 14 days prior to start of protocol therapy) and within 72 hours prior to the administration of any of the study drugs on dosing days. These blood draws may be performed at the same occasion as other laboratory tests obtained for the purpose of clinical monitoring of the patient. Patients who cross-over from Group 1 to Group 2 will need 4 additional blood draws pre-dose prior to their first 4 infusions of CDX-1127 (varlilumab) for immunogenicity and PK studies.
g:	A serum or urine pregnancy test is required within 24 hours of starting study treatment. If the pre-study assessment was performed within 24 hours prior to start of study treatment, a pregnancy test does not need to be repeated.
*:	Starting with Cycle 5 (Week 17), the dosage and administration schedule of nivolumab is changed to 480 mg every 4 weeks. The dosage and administration schedule of CDX-1127 (varlilumab) remains unchanged. Once the schedule of administration of nivolumab changes, the frequency of routine evaluations also changes accordingly to every 4 weeks as

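### The optional follow-up biopsy is timed at progression in some places and at end of study or off study in others, so the exploratory before/after tissue analyses can mix time points and populations

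*Combined protocol and SAP*

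**What the plan says.** Several places in the current protocol time the optional follow-up tissue:

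- **Section 9.1, text.** Tissue from a biopsy "at the time of suspected disease progression is optional", and mandatory only for Group 1 patients who cross over. The same section says the exploratory specimens are taken before treatment and at suspected progression, so that patients are not exposed to needless risk.
- **Section 9.1, exploratory table, optional FISH row.** "At the time of disease progression", for all patients.
- **Section 9.1, integrated table, optional CD27 row.** "At the end of study (for all patients". The optional IHC/CyTOF row in the exploratory table also says end of study, for all patients.
- **Section 10, Study Calendar.** Footnote c: "An off-study biopsy is optional for all groups". Footnote d: "Off-study evaluation to be performed 30 days (+/- 14 days) after the last dose of study drug".
- **Sections 5.4 and 5.5.** "Patients will be followed for additional 100 days (based on 5 half-lives) after end of therapy". Section 5.5 makes completion of that follow-up one of the events that remove a patient from the study.

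**The concern.** Section 9.1 gives the scientific purpose of the optional biopsies as "insights into whether patients progress despite increased immune cell infiltration into the tumor". That question needs tissue taken at progression. Yet the two rows that measure infiltration and CD27 are the ones not tied to progression, while the FISH row is.

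The rows differ in population as well as date. End of study for all patients takes in those who stop for toxicity and those who finish two years of treatment without progressing.

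Section 13.5 plans paired before/after tests (Wilcoxon signed rank, McNemar) and relates changes over time to clinical outcome. If sites follow different pages, the after value is a blend of progression, off-study and later samples, and the paired difference has no single meaning. Group 2 has no mandatory follow-up biopsy, so this optional sample is its only follow-up tissue. CD27 is the trial's one integrated biomarker.

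**Working it through.** **1. Is one shared sample intended?** Sections 9.2.1.2, 9.3.2.2, 9.3.3.2 and 9.3.6.2 each ask for at least 13 slides per collection time point and allow the tissue to be shipped together. The table rows give:

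- CD27: 3
- IHC/CyTOF: 7
- FISH: 1
- whole-exome sequencing: 2

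Sum: 3 + 7 + 1 + 2 = 13, which reproduces the stated minimum. It does so only if all four assays share one time point. Read row by row, the optional tissue needs 3 + 7 = 10 slides at end of study and 1 at progression. The optional sequencing row shows no time point. That may be a loss in text extraction and is not counted as an error.

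**2. How far apart are the timings?**

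| Source | Timing of the optional sample |
|---|---|
| 9.1 text; FISH row | suspected or documented progression |
| Calendar footnotes c and d | 30 − 14 = 16 to 30 + 14 = 44 days after last dose |
| CD27 and IHC/CyTOF rows, read through 5.4 and 5.5 | as late as about 100 days after end of therapy |

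**3. Must the sample precede the next therapy?** The bar on other anti-lymphoma treatment stands in Section 5.1, on agent administration. No matching statement covers the period after treatment ends, and no passage says the biopsy must come first. Section 9.1 foresees that some patients will go on to later trials.

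**4. How many patients?** Section 9.1 expects these biopsies in about 25% of patients, meaning Group 2 plus Group 1 patients who do not cross over. With 48 evaluable per group:

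- every Group 1 patient crosses over: 0.25 × 48 = 12 in total
- none crosses over: 0.25 × 96 = 24 in total

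The protocol gives no uptake figure for tissue from patients without progression.

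**5. What does not use this tissue?** The primary endpoint is overall response by LYRIC. The CD27 predictiveness curves (9.2.1.4) model response on treatment and CD27 and do not need follow-up tissue. Crossover biopsies are separately mandatory and timed at progression.

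**The case against.** The strongest reply is that this is loose terminology. Section 5.5 lists several triggers for leaving the study, one of them inability to follow the protocol as listed in Section 5.3, and 5.3 lists progression. The Study Calendar also speaks of removal from study for progressive disease. For a patient who stops because of progression, the timings can describe nearly the same event, and the text of 9.1 already states the intent. This stands in part: day 100 is one reading, not the protocol's statement. It does not help patients who stop for other reasons, and it leaves sites to choose.

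A reader might infer four stronger points that the documents do not support:

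- **Drug washout at the off-study visit.** Varlilumab is given every 4 weeks, so progression at the week-13 scan can fall 28 days after the week-9 dose. With the protocol's half-lives of 6 to 10.6 days, the fraction left is 2^(−28/6) = 4% to 2^(−28/10.6) = 16%. At day 30 it is 2^(−30/6) = 3% to 2^(−30/10.6) = 14%. The two are nearly the same, and serum decay does not measure tumour infiltrate.
- **Samples will follow new therapy.** This is inferred from silence. It can happen, but some of these biopsies are expected to serve eligibility for later trials, and those would come before the next treatment.
- **The groups become non-comparable.** Section 13.5 plans no comparison of Group 1 crossover tissue with Group 2 follow-up tissue.
- **Twelve samples per arm.** That requires essentially no crossover.

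It is also fair that limiting collection to progression would drop optional tissue from patients who never progress. The fix allows for this.

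**Conclusion.** The inconsistency is real and sits in current operative text. Its reach is limited to the exploratory before/after tissue comparisons, in about 12 to 24 patients in total. That count assumes the protocol's 25% uptake and 48 evaluable patients per group. How many samples would be mistimed cannot be known from the documents. The conclusion rests on the conflicting time points and on the difference in population, not on any residual-drug percentage. The point is minor: worth correcting because correction is cheap, with no bearing on the trial's main decision.

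**What to change.** - In the optional CD27 and IHC/CyTOF rows of Section 9.1, and in Study Calendar footnote c, set the optional sample at suspected progression and before any new anti-lymphoma therapy, in line with the 9.1 text and the FISH row. This is a condition on which samples count, not a rule on when other treatment may start.
- Check that the optional sequencing row carries the same time point.
- Record, for each sample, the days since the last dose of each drug and any intervening therapy.
- In Section 13.5, use only conforming samples in the progression-tissue paired analysis. Report any tissue from patients without progression separately.

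The cost is wording in two rows and one footnote, two data fields and a sentence in the analysis plan. No biopsy is added. The downside is a slightly smaller paired sample.
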